In May 2019, the EC requested a reassessment of the benefit-risk of tofacitinib pursuant to Article 20 of Regulation (EC) No 726/2004 due to a signal for increased risks of pulmonary embolism (PE) and mortality arising in an ongoing Pfizer-sponsored Phase 3b/4 safety study (A3921133: Phase 3b/4 Randomized Safety Endpoint Study of 2 Doses of Tofacitinib in Comparison to A Tumor Necrosis Factor (TNF) Inhibitor in Subjects with Rheumatoid Arthritis) designed to evaluate the risk of malignancy and major adverse cardiac events in RA patients aged 50 years and older who had at least one cardiovascular (CV) risk factor. In November 2019, the Committee on Human Medicinal Products (CHMP) concluded that, based on a recommendation from the Pharmacovigilance Risk Assessment Committee (PRAC), patients treated with tofacitinib are at increased risk of venous thromboembolism (VTE) events, both for deep vein thrombosis (DVT) as well as PE, especially in patients with risk factors for VTE. The PRAC further concluded that the risk of VTE events is dosedependent. To minimise this risk, the PRAC recommended that warnings be added to the Summary of Product Characteristics (SmPC) regarding the increased risk of VTE observed in patients taking tofacitinib, especially for patients with known risk factors for VTE. The PRAC also recommended that treatment with tofacitinib be discontinued in patients with suspected VTE and that tofacitinib 10 mg BID for maintenance treatment is not recommended in patients with UC who have known VTE risk factors, unless there is no suitable alternative therapy available. Clarifications on the posology were also added, particularly for UC patients in maintenance. Specifically, some patients (i.e., patients who failed to respond to alternative treatment options for UC such as TNF inhibitor treatment) who had a reduction in response to 5 mg BID maintenance treatment may benefit from an increase in maintenance dose to 10 mg BID; for these patients, the presence of known risk factors for VTE should be considered. However, to facitinib 10 mg BID for maintenance treatment should be used for the shortest duration possible.⁴

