In conjunction with the initial authorisation in March 2017, to minimise important potential and identified risks associated with the use of tofacitinib and to continue to monitor important potential and identified risks, the Marketing Authorisation Holder (MAH) implemented an educational programme designed to increase awareness of the risks of tofacitinib in each member state of the European Union (EU). This programme consists of routine (SmPC and patient package insert) and additional risk minimisation measures (a prescriber brochure, checklists for treatment initiation and treatment maintenance and a patient alert card to distribute to patients). There is also a website where healthcare professionals (HCPs) can access the aRMM materials.

The content and messages for the initial aRMM materials were agreed upon with the National Competent Authority prior to the launch of tofacitinib in each member state and the distribution of these materials was implemented after April 2017. Since then, the aRMM materials have been periodically revised to reflect subsequently approved indications. One revision incorporated the PRAC/CHMP's recommendations following the re-evaluation of the benefit-risk of tofacitinib (e.g., minimising the risk of VTE events among patients treated with tofacitinib), with distribution of these "Article 20-VTE-revised aRMM materials" to France on 04 May 2020 (termed "VTE aRMM materials" hereafter; Table 2). A subsequent revision incorporated the PRAC/CHMP's recommendations following the re-evaluation of the benefit-risk of tofacitinib (e.g., minimising the risk of CV events and malignancy among patients treated with tofacitinib), with distribution of these "CV and Malignancy-revised aRMM materials" to France on 17 May 2022 (termed "2021 signal evaluation procedure

aRMM materials" hereafter; Table 2). The newly updated aRMMs following the JAKi Article 20 referral were distributed on 06 April 2023.

Table 2. Dates for full reimbursement of tofacitinib and full distribution of the original, VTE aRMM materials, 2021 signal evaluation procedure aRMM materials and 2022/2023 JAKi referral aRMM materials in France

Country	Indication	Date of full reimbursement	Date of full distribution of the original aRMM materials	Start date of distribution of the VTE aRMM materials	Start date of distribution of the 2021 signal evaluation procedure aRMM materials	Start date of distribution of the 2022/2023 JAKi referral aRMM materials

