France	RA	September 2017	January 2018	04 May 2020	17 May 2022	06 April 2023
	PsA	December 2018	May 2019			
	UC	February 2019	May 2019			

A comprehensive plan was proposed to assess the effectiveness of the aRMM programme, which consists of the following 2 components:

- 1. Process indicators (i.e., HCPs' receipt and understanding of the aRMM materials); and
- 2. Outcome indicators (i.e., prescribing and clinical practice behaviours with respect to recommendations).

To assess these 2 components, the MAH proposed the following post-authorisation safety studies with the aim of evaluating the effectiveness of the aRMM programme:

- 1. A survey of tofacitinib prescribers to address component 1 (A3921334, completed); and
- 2. A drug utilisation study (DUS) (Study A3921321) to address component 2 that will assess prescribing patterns of tofacitinib and whether prescribers are adherent to the screening and monitoring recommendations and limitations for use included in the aRMM materials for patients prescribed tofacitinib.

As a result of the Article 20 benefit-risk reassessment, the MAH will additionally evaluate HCPs' adherence to the new PRAC recommendations and limitations for use to minimise the risk of VTE across all approved indications (i.e., tofacitinib should be used with caution in patients with known VTE risk factors regardless of indication and dosage), with additional focus on the use of tofacitinib 10 mg BID as a maintenance treatment for patients with UC, and use and prior treatments among patients aged 65 years and older treated with tofacitinib. The MAH will also examine tofacitinib prescribing patterns over time, as well as changes in the utilisation of tofacitinib among patients with VTE risk factors and among elderly patients aged \geq 65 years following the updated recommendations and limitations for use. As a result of the 2021 signal evaluation procedure, the MAH will also assess HCPs' adherence to the

new EMA recommendations and limitations for use related to tofacitinib use in patients with CV risk factors and use in patients with malignancy risk factors. Similar to above, the MAH will also examine tofacitinib prescribing patterns over time in the context of the 2021 signal evaluation procedure outcome. As a result of the 2022/2023 JAKi Article 20 referral, the MAH will assess HCPs' adherence to the updated recommendations and limitations for use related to tofacitinib use in patients with VTE, CV or malignancy risk factors.

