9.3. Variables

9.3.1. Variables and definitions

Table 3 summarises and defines the study variables to be collected and analysed in SNDS. Unless otherwise specified, these variables will be assessed during each patient's entire study period (baseline period and follow-up period).

This study will use code-based algorithms from the literature and/or other code lists to identify study variables. Published validated algorithms will be used where available.^{6, 7} All code-based algorithms and code lists will be reviewed and/or approved by Pfizer prior to

study initiation. Preliminary algorithms and/or codes are proposed in the following (Table 3); see also Annexes). Final algorithms and/or code lists may be refined as part of the statistical analysis plan (SAP) development. It is also to be noted that while laboratory tests performed are captured, results of laboratory tests are not available in the SNDS database.

Table 3. Operational definitions of study variables in Système National des Données de Santé

Variable	Role	Operational definition
Exposure		
Tofacitinib treatment	Exposure	Defined as having ≥1 ATC code (L04AA29) for a reimbursed prescription of tofacitinib during the indexing period. Index date is defined as the date of the first reimbursed prescription of tofacitinib.
Indication		
Indication	Indication (including off-label use)	Reported in the following categories: RA, PsA, UC and off-label/unknown based on hospital discharge diagnoses and active registration for diagnoses reported in the long-term disease (LTD) database for outpatients in the relevant time period. If there are no diagnosis codes for RA, PsA or UC, it will be categorised as off-label/unknown indications. Details will be further developed in the SAP.
		List of diagnoses codes for indications in ANNEX 13. LIST OF DIAGNOSIS CODES FOR INDICATIONS.
Primary Objective 1: I	Demographics, comorbi	dities and prior and current medications
		T OF CODES FOR COMORBIDITIES, unless otherwise
Age at tofacitinib initiation	Demographic	Calculated as the date of tofacitinib initiation minus the patient's month and year of birth and reported in the following categories: <18 years, 18-29 years and 30-39 years; 40-49 years; 50-59 years; 60-69 years; 70-79 years; ≥80 years; and <65 years and ≥65 years.
Sex	Demographic	Reported in the following categories: Male, Female and Unknown. Assessed on the date of the index tofacitinib prescription dispensing.

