Initiating tofacitinib with ≥1 VTE risk factor(s)	Outcome: changes in use in patients with VTE risk factors	Defined as ≥1 VTE risk factor(s) (as listed and defined above) identified in the 12 months prior to the index tofacitinib dispensing.
Initiating tofacitinib with ≥1 VTE risk factors other than CV or malignancy risk factors	Outcome: changes in use in patients with VTE risk factors	The same definition as above but only limited to VTE risk factors other than CV or malignancy risk factors.
VTE risk factor scores	Outcome: changes in use in patients with VTE risk factors	Calculated as the sum of the number of VTE risk factors (as listed and defined above) identified in the 12 months prior to the index tofacitinib dispensing. Weighting of VTE risk factors may be considered as a sensitivity analysis to reflect the potential different
Number of UC patients with: ≥1 VTE risk factor; no prior alternative therapy (i.e., biologic); and an ADD >10 mg in Weeks 17-24, Weeks 25-32, Weeks 33-40 or Weeks 41-48 of follow-up	Outcome: changes in use in patients with VTE risk factors	importance of each risk factor. Defined as an UC patient meeting all of the following criteria: ≥1 VTE risk factor(s) (as listed and defined above) 12 months prior to the index tofacitinib prescription dispensing; 0 prescription medication dispensing for a biologic (as identified by ATC codes) in the 12 months prior to the index tofacitinib prescription dispensing; and an ADD of >10 mg in any of the intervals: Weeks 17-24, Weeks 25-32, Weeks 33-40 and Weeks 41-48 of follow-up (ADD defined in Section 9.3.3). Complete list of biologics in ANNEX 7. LIST OF ATC CODES FOR MEDICATIONS OF INTEREST TO AVOID WHILE TAKING TOFACITINIB.
Assessment of VTE risk; Section 9.3.2)	factors while receiving	tofacitinib therapy (duration of tofacitinib therapy defined in
VTE	Outcome: changes in use in patients with VTE risk factors	Defined as ≥1 ICD-10 diagnosis code for VTE while receiving tofacitinib therapy. List of VTE codes in ANNEX 12. LIST OF DIAGNOSIS CODES FOR VTE

Table 3. Operational definitions of study variables in Système National des Données de Santé

Variable	Role	Operational definition
Surgery, major	Outcome: changes in use in patients with VTE risk factors	Defined as ≥1 procedure code for a major surgery while receiving tofacitinib therapy.
MI	Outcome: changes in use in patients with VTE risk factors	Defined as ≥1 ICD-10 diagnosis code for an MI while receiving tofacitinib therapy.

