Heart failure	Outcome: changes in use in patients with VTE risk factors	Defined as ≥1 ICD-10 diagnosis code for heart failure while receiving tofacitinib therapy.
Use of combined hormonal contraceptives or hormonal replacement therapy	Outcome: changes in use in patients with VTE risk factors	Defined as ≥1 prescription dispensing of a combined hormonal contraceptives and/or hormonal replacement therapy (as identified by ATC codes) while receiving tofacitinib therapy.
Inherited coagulation disorder	Outcome: changes in use in patients with VTE risk factors	Defined as ≥1 ICD-10 diagnosis code for inherited coagulation disorder while receiving tofacitinib therapy.
Malignancy (non- metastatic and metastatic, excluding NMSC)	Outcome: changes in use in patients with VTE risk factors	Defined as ≥1 ICD-10 diagnosis code for malignancy (excluding NMSC) while receiving tofacitinib therapy.
Age ≥ 65 years	Outcome: changes in use in patients with VTE risk factors	Defined as age ≥65 years while receiving to facitinib.
Diabetes	Outcome: changes in use in patients with VTE risk factors	Defined as ≥1 ICD-10 diagnosis code for diabetes or ≥3 (or at least 2 in case of large pack sizes) prescription dispensing of oral antidiabetic agents and/or insulin (identified by ATC codes) while receiving tofacitinib therapy.
Hypertension	Outcome: changes in use in patients with VTE risk factors	Defined as ≥1 ICD-10 diagnosis code for hypertension or ≥3 (or at least 2 in case of large pack sizes) prescription dispensing of antihypertensive agents (identified by ATC codes) while receiving tofacitinib therapy.
Discontinuation of tofacitinib after developing ≥1 VTE risk factors while taking tofacitinib	Outcome: changes in use in patients with VTE risk factors	Defined as ≥1 VTE risk factor(s) while receiving tofacitinib therapy (as listed and defined above) plus 0 prescription dispensing for tofacitinib within a specific time window after the code for the first VTE risk factor.
g		Note: The time window for when to look for a tofacitinib prescription dispensing will be specific to the VTE risk factor(s) acquired while receiving tofacitinib therapy and will be operationalised during SAP development.
		Duration of tofacitinib therapy defined in Section 9.3.2.

Table 3. Operational definitions of study variables in Système National des Données de Santé

Variable Role Operational definition	
Discontinuation of Outcome: changes The same definition as above but of	only limited to VTE risk

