9.7. Data analysis

Descriptive statistics will be provided for all results. Categorical variables will be reported using frequency distributions. Ordinal variables will be reported using frequency distributions, means, standard deviations (SDs), minimums, 25th percentiles, medians, 75th percentiles and maximums, unless otherwise specified. Continuous variables will be reported

using means, SDs, minimums, 25th percentiles, medians, 75th percentiles and maximums, unless otherwise specified. When relevant, 95% CIs will be calculated for the study outcomes outlined in Section 9.3.1 (Outcomes) and Table 3. All analyses will be stratified by the approved indication or indication groups ("RA or PsA" and "UC"), unless otherwise specified. In addition, for the objective of "Describe prescribing patterns over time", comparative statistical analyses will be conducted to describe changes in the use of tofacitinib across reporting periods to assess the statistical significance of reductions in the use of tofacitinib among patients with risk factors (see below for further details). P-value < 0.05 indicates statistical significance.

Missing values will be reported as missing and no imputation will be undertaken. Results will be summarised in tables and figures in Microsoft® Excel and/or Word format.

Detailed methodology for summary and statistical analyses of data collected in this study will be documented in a SAP, which will be dated, filed and maintained by the sponsor. The SAP may modify the plans outlined in the protocol; any major modifications of primary endpoint definitions or their analyses would be reflected in a protocol amendment.

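### As written, neither discontinuation/continuation pair isolates stopping after an on-treatment VTE: both pool VTE with other factors and start the window at the first one

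*Protocol*

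**What the plan says.** Section 7 reports: "The PRAC also recommended that treatment with tofacitinib be discontinued in patients with suspected VTE". It then says of the aRMM materials: "One revision incorporated the PRAC/CHMP's recommendations following the re-evaluation of the benefit-risk of tofacitinib". It commits the MAH to evaluate "adherence to the new PRAC recommendations and limitations for use to minimise the risk of VTE across all approved indications", and the parenthesis that follows explains this as: "tofacitinib should be used with caution in patients with known VTE risk factors regardless of indication and dosage".

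Table 3 in Section 9.3.1 lists ten VTE risk factors to be assessed while the patient receives tofacitinib: VTE, major surgery, MI, heart failure, hormonal contraception or replacement therapy, inherited coagulation disorder, malignancy, age ≥65, diabetes and hypertension. Discontinuation requires one or more of these "plus 0 prescription dispensing for tofacitinib within a specific time window after the code for the first VTE risk factor". Continuation uses the same anchor with at least one dispensing. A second pair applies the same definition, limited to VTE risk factors that are not CV or malignancy risk factors. A note leaves the window length to the SAP, to be set according to the factor acquired.

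Section 9.7.2.4.1 reports the proportions discontinuing and continuing after one or more factors. It asks for tabulation by individual factor only for factors found before initiation.

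Section 9.3.1 also says "Final algorithms and/or code lists may be refined as part of the statistical analysis plan (SAP) development", and Section 9.7 says "The SAP may modify the plans outlined in the protocol".

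**The concern.** The listed factors do not carry the same advice. For VTE, Section 7 reports a recommendation to stop. For age ≥65, CV factors and malignancy factors it reports use only where no suitable alternative exists. For VTE risk factors generally it reports caution. A pooled proportion mixes these, so continuing after a VTE, which runs against the stop advice, looks the same as continuing after starting a hormonal contraceptive.

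The anchor adds a second problem. If another factor is coded before the VTE, the window opens at that earlier code, and a routine fill between the two events settles the classification. A patient who stopped at the VTE can then be reported as having continued. At stake is whether the report can show what prescribers did when a VTE occurred on treatment.

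**Working it through.** The protocol gives no figure for this outcome, so there is none to reproduce. The check is a comparison of definitions, with arithmetic for size.

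**1. Pooling.** The main pair has ten factors. The Table 3 CV list removes age ≥65, MI (within coronary artery disease), diabetes and hypertension. The malignancy list removes malignancy, and age again. Ten minus five leaves five: VTE, major surgery, heart failure, hormonal therapy and inherited coagulation disorder. VTE stays pooled in both pairs. These are counts of list items, not patients.

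**2. Anchor, worked example.** Major surgery is itself a qualifying factor: "Defined as ≥1 procedure code for a major surgery while receiving tofacitinib therapy". Take surgery on day 100, a fill on day 112, pulmonary embolism on day 130 and no later fill.
- Counting from surgery, the fill comes 112 − 100 = 12 days later. If the SAP's surgery window is at least 12 days, the patient counts as continuing in both pairs.
- Counting from the embolism, there are no fills, so the patient counts as discontinuing.

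A patient whose first or only factor is the VTE is classed correctly, but is not visible apart from the pool.

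**3. Misclassified share within that sequence.** Suppose fills occur every f days, the first fill after the earlier factor is uniform on (0, f), the window is at least f, and treatment stops at the VTE. Then P(classed as continuing) = min(1, gap/f).

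| Days from earlier factor to VTE | f = 28 (assumed) | f = 56 (assumed) |
|---|---|---|
| 7 | 25% | 12.5% |
| 14 | 50% | 25% |
| 21 | 75% | 37.5% |
| 30 | 100% | 54% |

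These are shares within the sequence only. The documents do not show how often the sequence occurs.

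**4. Size of a VTE-specific row.** Inputs: about 8,000 RA/PsA and 2,000 UC initiators (Section 9.5); a 360-day year (Table 3); a 90-day window, echoing the grace-period example in Section 9.3.2; on-treatment VTE in 0.5-2% of patients (assumed); VTE timing uniform over follow-up (assumed).
- Share of VTEs with a full window W inside follow-up = (360 − W)/360. For W = 30, 60, 90 and 120 this is 92%, 83%, 75% and 67%. The full window is needed: with 28-day fills a continuing patient's last visible fill is on day 336, so a VTE from day 337 would look like discontinuation.
- RA/PsA: 8,000 × 0.005 × 0.75 = 30, to 8,000 × 0.02 × 0.75 = 120.
- UC: 2,000 × 0.005 × 0.75 = 7.5, to 2,000 × 0.02 × 0.75 = 30.
- Together: 37.5 to 150. The 95% half-width at 50% is 1.96 × √(0.25/n), which is 16.0 points at n = 37.5 and 8.0 points at n = 150.

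**5. By VTE reporting period.** Section 9.2.2 excludes UC starts before May 2019, and VTE period 1 ends on 31 May 2019, so UC has one month in it. Spreading 1,000 UC starts evenly over May 2019 to December 2020 (20 months) and the other 1,000 over the next 48 months gives 50, 850 and 1,100 patients. Multiplying by 0.00375 to 0.015 gives about 0.2-0.8, 3-13 and 4-17 evaluable VTEs. RA/PsA, spread evenly as 4,000 over 36 months and 4,000 over 48, gives 1,889, 1,889 and 4,222 patients, or about 7-28, 7-28 and 16-63 VTEs. The RA/PsA total and period 1 count are upper bounds, because PsA starts before May 2019 are also excluded (Table 2, Section 9.2.2).

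**The case against.** The strongest reply is that this belongs to the SAP. Factor-specific windows require the analyst to know which factor each patient acquired, on-treatment VTE is already a Table 3 variable, and the SAP may refine algorithms or modify plans. That stands to the extent that nothing is locked and the repair is easy. But the note defers only the window. The pooled condition and the first-factor anchor are written into the protocol's own definition, and a factor-specific window length cures neither.

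The second reply is that the protocol does not promise this outcome. The stated objective is use in patients with VTE risk factors, and the explanatory parenthesis in Section 7 names caution, not stopping at a VTE. This also stands. That the French materials carry the stop advice is inferred from the statement that they took up the PRAC/CHMP recommendations. A reader might infer that the protocol breaks an explicit commitment to measure stopping after VTE; the text does not go that far.

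A reader might also infer that all the other factors carry only a caution. That does not hold for the main pair, because Section 7 restricts use at age ≥65 and with CV or malignancy factors to patients without suitable alternatives. Finally, small cells make some pooling of rare events defensible, though they do not require mixing VTE with other factors.

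**Conclusion.** The point holds as a cheap improvement of low priority. As the definitions stand, no stated output shows whether tofacitinib was stopped after an on-treatment VTE, and patients with an earlier factor can be put in the wrong category. The outcome is descriptive. The primary comparison in Section 9.5, the proportion of initiators with risk factors in period 3 against period 1, does not use these variables, so a reading that the study's main result is compromised has no support. Nor are VTE patients misclassified in general: the error needs another factor first, then a fill, then the VTE with treatment stopped. The sizes rest on the assumed VTE frequency, fill interval, window, VTE timing and even accrual. Under them, an overall descriptive estimate is feasible, RA/PsA by period is weak at the low end, and UC supports no before/after comparison.

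**What to change.** Add one descriptive row to Table 3 and Section 9.7.2.4.1. Among patients with a first Annex 12 VTE code while receiving tofacitinib, report the proportions with 0 and with ≥1 tofacitinib dispensings in a window after that code, regardless of earlier factors. Limit it to patients whose full window lies within the 12-month follow-up. Report it first pooled over periods and indication groups, and by VTE reporting period only where cells exceed 5, in line with Section 9.4. Keep the existing pairs unchanged.

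State two limits with the row: a coded VTE only approximates a suspected one, and patients without 12 months of post-index data, probably including early deaths from VTE, are not captured.

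The cost is one derived variable and one table from codes and dispensings already planned. Reporting the existing pairs without VTE as well is optional and is extra work, since the first-factor anchor must be derived again for four variables. The downsides are small cells, about 25% of VTEs lost to a 90-day full-window rule, and VTE not coded in hospital or LTD data remaining invisible.
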